#### **Analysis:**

##### **Milestone 1:**

Consider the demographic, patient, and disease characteristics of all eligible tofacitinib initiators in **Table 1**. Categorical variables will be examined using frequencies and proportions. Continuous variables will be summarized using descriptive statistics (mean, standard deviation, minimum, 25% percentile, median, 75% percentile, maximum).

In **Table 2**, we will present the therapy status of initiators at the six-month follow-up visit.

**Table 3** will examine the outcomes of interest at the six-month follow-up visit. Binary outcomes will be presented as response rates with 95% CI using normal approximation to binomial proportions, and summary statistics (n, mean (SD), [P0,P25,P50,P75,P100]) baseline, six-month, and change in continuous outcomes will also be presented.

### Milestone 2:

The analyses stratified by mono- and combination therapy for this milestone will be completed when the sample reaches at least 100 initiators in both mono- and combination therapy groups.

Consider the demographic, patient, and disease characteristics of the tofacitinib monotherapy and combination therapy initiators in **Table 4**. Categorical variables will be examined using frequencies and proportions, and, when sample size allows for significance testing, differences across therapy patterns will be tested using chi-square or Fisher exact tests. Continuous variables will be summarized using descriptive statistics (n, mean, standard deviation, minimum, 25% percentile, median, 75% percentile, maximum). When sample size allows for significance testing, differences across therapy groups will be tested using Wilcoxon rank sum tests.

In **Table 5**, we will present the therapy status of initiators at the six-month follow-up visit.

**Table 6** will examine the outcomes of interest at the six-month follow-up visit. The change from baseline to six months in continuous outcomes will be analyzed using an analysis of covariance model with fixed effects for treatment group and baseline value. For continuous outcomes, we will not impute missing values. Also, for those discontinuing therapy prior to follow-up, we will use the value immediately prior to discontinuation as the follow-up value. We will present LS Means (standard error) for each therapy group as well as the difference in the LS Means (standard error), 95% CI and p-value. Binary outcomes will be presented as response rates with 95% CIs using normal approximation to binomial proportions. We will provide comparisons of response rates between groups with 95% CIs and p-values using normal approximation for the difference in binomial proportions. As a supportive analysis, treatment difference between the groups will be assessed using logistic regression models with treatment group as the sole covariate. For binary outcomes, we will impute non-response for missing values and for those patients discontinuing therapy prior to follow-up.

In **Table 7**, we will present summary statistics (n, mean (SD), [P0,P25,P50,P75,P100]) for continuous outcomes featured in Table 3 at baseline, six months, and the difference from baseline to six months overall and by therapy group.

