5. AMENDMENTS AND UPDATES

Amendment number	Date	Protocol section(s) changed	Summary of amendment(s)	Reason
1	24May2023	9.3	Administrative change regarding CDAI and cDAPSA values	The values for CDAI and cDAPSA are being pulled from the database. Pfizer will not do any recalculation post-hoc
1	24May2023	9.5	Planned sample size reduced from 100 to 80 patients per group Substantial Amendment	Based on CorEvitas estimates and current enrollment pattern, it is estimated that it will take approximately 12 months to get to at least 80 patients per group.
1	24 May 2023	3	Adding Author (PPD) address and new PPD PPD	NY Pfizer offices changed
1	24 May 2023	6	Interim report 3, end of data collection, and final study report dates were updated	Update due to the amendment
2	02Oct2023	9.5	Planned sample size reduced from 80 to 73 patients per group Substantial Amendment	Based on CorEvitas estimates and current enrollment pattern, it is estimated that it will take approximately 12 months to get to at least 73 patients per group.

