9.5. Study Size

This is an estimation study and not hypothesis testing study. Precision estimates indicate that approximately 80-73 patients with 12 months of follow-up are needed per group to achieve reasonably precise estimates for the outcomes of interest. For binomial proportions, a sample size of 80-73 patients per group would yield a half width of the 2-sided 95% confidence interval (CI) to be less than 11 percentage points for the binomial proportions, and less than 16 percentage points for the difference in 2 binomial proportions.

As of October 1, 2020, there are 160 tofacitinib initiators within the CorEvitas registry of whom 93 have a 6 month follow-up visit. The first objective of the study will be assessed using the latest data cut available once the protocol is approved and will be reported in the first interim report. The stratifications by mono and combination therapy listed in the second objective will be reported in subsequent interim reports as sample sizes reach appropriate thresholds. For comparative analyses, this will be at least 80-73 patients per arm. Precision estimates will be used to determine appropriate sample sizes for the descriptive analyses. The final report will be issued once all subgroups reach the minimal sample sizes to ensure sufficient precision in the estimates of the outcomes.

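### The SAP still starts the monotherapy versus combination analysis at 100 per group, while the amended protocol starts it at 73; neither trigger names the 6-month visit, and the stated precision fits 80 rather than 73.

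*SAP*

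**What the plan says.** **SAP, Milestone 2.** The analyses stratified by mono- and combination therapy "will be completed when the sample reaches at least 100 initiators in both mono- and combination therapy groups". Milestone 2 includes the between-group comparisons in Table 6.

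**Protocol, section 5.** Amendment 1 (24 May 2023): "Planned sample size reduced from 100 to 80 patients per group". Amendment 2 (2 October 2023): "Planned sample size reduced from 80 to 73 patients per group". Both are labelled substantial.

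**Protocol, section 9.5.** "For comparative analyses, this will be at least 80-73 patients per arm". Also: "The final report will be issued once all subgroups reach the minimal sample sizes". The same section says that this number of "patients with 12 months of follow-up are needed per group to achieve reasonably precise estimates for the outcomes of interest". It promises a 95% CI half-width under 11 points for one proportion and "less than 16 percentage points for the difference in 2 binomial proportions".

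**Eligibility.** Protocol section 9.2.1 and the SAP Study Cohort section both require a follow-up visit at 6 (±3) months. Both documents also use the word initiators for people counted before that visit. Section 9.5 reports "160 tofacitinib initiators within the CorEvitas registry of whom 93 have a 6 month follow-up visit". The SAP feasibility table (October 2021 registry version) lists 132 monotherapy and 81 combination initiators, of whom 59 and 55 have the visit.

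**Annex 1 of the protocol** lists a SAP dated 20 August 2021.

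**The concern.** The two documents give different thresholds for the same analysis. The trigger decides when Objective 2 is analysed and, through section 9.5, when the final report can be issued. Both amendments lowered the size because of the enrolment pattern, so a SAP still set at 100 works against their stated purpose. An analyst following the SAP would hold the analysis after the protocol had released it.

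Two further points in the same text need attention. The counting unit is not written into either trigger sentence, and section 9.5 names a follow-up length that is not the one in the objectives. The precision statement was also kept unchanged when the size fell to 73, so a reader may rely on bounds that the current size does not guarantee.

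**Working it through.** **1. The trigger.** Inputs: 100 (SAP Milestone 2), 73 (protocol sections 5 and 9.5), and 59 monotherapy and 55 combination patients with a six-month visit (SAP feasibility table, October 2021).

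| Still needed from that cut, counting patients with the visit | Mono | Combo |
|---|---|---|
| To reach 73 (protocol) | 73 − 59 = 14 | 73 − 55 = 18 |
| To reach 100 (SAP) | 100 − 59 = 41 | 100 − 55 = 45 |
| Difference | 27 | 27 |

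The difference of 100 − 73 = 27 per group does not depend on the cut. The shortfalls do, and they will have shrunk since October 2021. The documents give no accrual rate by group, so the delay cannot be put into months.

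**2. Which unit the protocol counts.** In October 2021 there were already 132 and 81 initiators counted before the visit, above both 80 and 73. Yet the amendments of May and October 2023 each expect about 12 months to reach at least 80, then at least 73, per group. Those statements make sense only if patients with follow-up are counted.

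**3. The precision statement.** Section 9.7 and the SAP specify normal-approximation intervals. No response rate is given, so I take the worst case, p = 0.5, as an assumption.

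- One proportion: half-width = 1.96 × √(p(1−p)/n)
- Difference, equal n and equal p: half-width = 1.96 × √(2p(1−p)/n)

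| n per group | One proportion (stated: <11) | Difference (stated: <16) |
|---|---|---|
| 80 | 1.96 × √(0.25/80) = 10.96 | 1.96 × √(0.5/80) = 15.49 |
| 73 | 1.96 × √(0.25/73) = 11.47 | 1.96 × √(0.5/73) = 16.22 |
| 100 | 9.80 | 13.86 |

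The plan's bounds are reproduced at 80 and missed at 73. The smallest sizes that meet them at p = 0.5 are 1.96² × 0.25/0.11² = 79.4, so 80, and 1.96² × 0.5/0.16² = 75.03, so 76.

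**4. Response rates for which the bounds do hold at 73.**

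- One proportion: p(1−p) ≤ 73 × (0.11/1.96)² = 0.2299, so p at most 0.358 or at least 0.642.
- Difference, equal p: p(1−p) ≤ 73 × (0.16/1.96)²/2 = 0.2432, so p at most 0.417 or at least 0.583.

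**The case against.** **The SAP is allowed to differ.** Section 9.7 lets the SAP modify the protocol's plans. That is so, but 100 is exactly the size before Amendment 1 and the SAP gives no reason for keeping it, so a deliberate choice is unlikely. This is an inference: the SAP's own date is not visible in the text reviewed. Annex 1 does not settle it, because the SAP text uses an October 2021 registry version and so postdates the 20 August 2021 listing.

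**The visit is already implied.** It is an eligibility criterion in both documents, so it is not missing from the plan. This largely stands. What remains is a wording gap, because both documents also use initiators for people counted before the visit.

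**The precision miss is trivial.** It is about 0.5 and 0.2 points, in an estimation study whose text says approximately, and it vanishes for rates far enough from 0.5. This stands as to size. The bounds nevertheless fit the previous size and not the current one, and no response rate is stated to rescue them.

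**Stronger readings that the documents do not support.**

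- A reader might infer that the SAP trigger could fire too early, with fewer than 73 evaluable patients, because monotherapy already had 132 initiators. The amendment timelines point to counting patients with follow-up, and the SAP's 100 matches the protocol's former 100, which suggests the same unit. Applying the 44.7% visit rate to 100 monotherapy initiators gives a state that cannot occur, since 59 already had the visit.
- A reader might take 80-73 in section 9.5 for a range or an error. It is probably strike-through lost when the PDF was read, and the amendment log makes 73 the current figure.
- Six of the seven binary outcomes in Table 6 are assessed only among patients not already in the target state, so their precision is lower. The documents give no baseline proportions from which to size this, and it would apply at 73, 80 or 100 alike.

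**Conclusion.** The inconsistency is real and should be fixed. The SAP threshold for Objective 2 is 27 patients per group above the amended protocol's, and the supported consequence is delay to that analysis and possibly to the final report. Eligibility and the Objective 1 analysis are not affected. The delay assumes that patients with the 6 (±3) month visit are counted, which is the reading the documents favour.

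The precision statement needs a small correction. At 73 per group and p = 0.5 the half-widths are about 11.5 and 16.2 points against stated bounds of 11 and 16. This part is conditional on the response rate, which the documents do not give. The 12-month follow-up wording is a separate slip in the same section that leaves the counted population unclear.

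**What to change.** - In SAP Milestone 2 and protocol section 9.5, use one identical trigger: at least 73 eligible patients per group with a 6 (±3) month follow-up visit.
- In section 9.5, reconcile the 12-month follow-up wording with the 6-month objectives.
- In section 9.5, restate precision at 73 per group as about 11.5 points (one proportion) and 16.2 points (difference) at p = 0.5. Alternatively, keep the bounds of 11 and 16 and state the response rates under which they hold: at most 0.358 or at least 0.642 for one proportion; at most 0.417 or at least 0.583 for the difference with equal rates.
- Add that precision is lower for outcomes assessed only among patients not already in the target state at baseline.
- Cite the updated SAP, with its date, in Annex 1.

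The cost is text edits to the SAP and protocol and a slightly less favourable stated precision. No extra patients are required.

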9.7. Data Analysis

Detailed methodology for summary and statistical analyses of data collected in this study will be documented in a statistical analysis plan (SAP), which will be dated, filed and maintained by the sponsor. The SAP may modify the plans outlined in the protocol; any major modifications of endpoint definitions or their analyses would be reflected in a protocol amendment.

In general, the data for all continuous endpoints will be summarized by timepoint and treatment group in tables containing descriptive statistics (N, mean, standard deviation, standard error of the mean, minimum, 1st, 2nd (ie, median) and 3rd quartiles and maximum) for baseline and change from baseline/percent change from baseline for those endpoints measured at baseline. The data for all categorical endpoints will be summarized by contingency tables that show the counts/frequency in the various categories by treatment group at each timepoint.

For binary endpoints, 95% CI using normal approximation to binomial proportions will be provided for each group. The 95% CI will also be provided for comparisons between groups using normal approximation for the difference in binomial proportions.

Continuous endpoints (eg, HAQ-DI) at month 6 will be analyzed as change from baseline with an analysis of covariance (ANCOVA) model that includes treatment and baseline value as covariates. Comparisons between groups will be performed using 95% CI.

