At the six-month follow-up visit, the following will be assessed:

Among those not in the specified disease activity state, achievement of:

- Minimal Disease Activity
- Body Surface Area Score of 0
- PASDAS < 3.2
- Resolution of enthesitis
- Resolution of dactylitis
- Clinical Global Assessment of PsO – achievement of “Clear” or “Almost Clear”

Baseline to six months change in:

- cDAPSA
- DAPSA
- PASDAS
- HAQ-DI
- Low Disease Activity as defined by cDAPSA (cDAPSA ≤ 13)
- BSA
- CDAI
- Tender joint count (68)
- Swollen joint count (66)
- Patient global skin assessment
- Patient pain
- Patient fatigue
- Clinical Global Assessment of PsO
- WPAI Domains

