**Table 5. Therapy status six months post-initiation**

	Overall	Mono	Combo	p -value a
All Patients, N				
Remain on tofacitinib, n (%)				
Discontinued tofacitinib, n (%) b				
Switched to a bDMARD, n (%) c				
Added OSM, n (%)				
Discontinued OSM, n (%)				

a p-value from chi-square testb This group consists of those discontinuing tofacitinib and not initiating a bDMARD at or prior to the six-month follow-up visitc This group consists of those discontinuing tofacitinib and initiating a bDMARD at or prior to the six-month follow-up visit

**Table 6.** Disease activity outcomes at six months

	Mono	Combo	Mono vs Combo		
	Binary Outcomes	Response Rate (95% CI) a	Response Rate (95% CI) a	Rate Difference (95% CI) a	p-value a
Achievement of:					
LDA (cDAPSA)					
Minimal Disease Activity					
Body Surface Area Score of 0					
PASDAS < 3.2					
Resolution of enthesitis					
Resolution of dactylitis					
Clinical Global Assessment of PsO – Clear or Almost Clear					
Continuous Outcomes		LS Means (SE)	LS Means (SE)	Δ LS Means (SE) 95% CI	
Baseline to six-month change in:					
cDAPSA					
DAPSA					
PASDAS					
HAQ-DI					
BSA					
CDAI					
Tender joint count					
Swollen joint count					
Patient global skin assessment					
Patient pain					
Patient fatigue					
Clinical Global Assessment of PsO					
Work Time Missed					
Impairment While Working					
Overall Work Impairment					
Activity Impairment					

a 95% CI for the response rate and 95% CI and p-value for the rate difference were based on normal approximation to binomial proportions. OR (95% CI) was based on a logistic regression model with treatment group as the sole covariate

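### Normal-approximation intervals are the only ones planned for response rates and differences, though restricted outcomes such as dactylitis resolution may rest on few patients per group

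*SAP*

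**What the plan says.** The normal approximation is specified wherever an interval for a binary outcome is planned.

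- Protocol 9.7, single rates: "95% CI using normal approximation to binomial proportions will be provided for each group". Differences: "The 95% CI will also be provided for comparisons between groups using normal approximation for the difference in binomial proportions".
- SAP Milestone 1 (Table 3): "Binary outcomes will be presented as response rates with 95% CI using normal approximation to binomial proportions".
- SAP Milestone 2 (Table 6), single rates: "Binary outcomes will be presented as response rates with 95% CIs using normal approximation to binomial proportions". Differences: "We will provide comparisons of response rates between groups with 95% CIs and p-values using normal approximation for the difference in binomial proportions".
- Footnote to SAP Table 6: "95% CI for the response rate and 95% CI and p-value for the rate difference were based on normal approximation to binomial proportions".

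No minimum count, exact or score alternative, or fallback is given for these outcomes. Fisher's exact test appears only for baseline comparisons. The supportive logistic regression gives an odds ratio, not an interval for a rate or a rate difference.

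The SAP list of six-month outcomes introduces six responder outcomes with "Among those not in the specified disease activity state, achievement of". They are MDA, BSA of 0, PASDAS below 3.2, resolution of enthesitis, resolution of dactylitis, and clear or almost clear skin. The natural reading is that the restriction applies at baseline.

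**The concern.** Dactylitis or enthesitis can resolve only in patients who have it, so those Table 6 rows use a subset of each therapy group. With few patients the Wald interval covers less often than it claims, chiefly when the rate is near 0 or 1. There it can also have impossible limits, or no width at all. Under Milestone 2, missing values and discontinuations count as non-response, which lowers responder counts and makes near-empty cells more likely.

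Protocol 9.5 describes an estimation study, so the intervals are its main product. For an affected row the printed 95% would be wrong, and a Wald difference could exclude zero where a small-sample interval does not.

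**Working it through.** **The plan's own figure.** Protocol 9.5 gives half-widths below 11 points for a proportion and below 16 for a difference. At p = 0.5 the formulas are 1.96·√(0.25/n) and 1.96·√(0.5/n).

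- n = 80: 10.96 and 15.49 points, which reproduces the statement.
- n = 73: 11.47 and 16.22 points, which does not.

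That mismatch is a separate matter. What counts here is that the precision statement refers to whole groups.

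**Inputs.** Group size is 73 (protocol amendment 2), or 100 from the SAP Milestone 2 trigger. The qualifying share is not in the documents; 15, 20 and 30% are assumed:

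- 0.15, 0.20, 0.30 × 73 = 11, 15, 22
- 0.15, 0.20, 0.30 × 100 = 15, 20, 30

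**Formulas** (z = 1.96).

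- Wald, one rate: p̂ ± z·√(p̂(1−p̂)/n).
- Wilson, one rate: [p̂ + z²/2n ± z·√(p̂(1−p̂)/n + z²/4n²)] / (1 + z²/n).
- Wald, difference: d ± z·√(p̂₁(1−p̂₁)/n₁ + p̂₂(1−p̂₂)/n₂).
- Newcombe, with Wilson limits l and u: from d − √((p̂₁−l₁)² + (u₂−p̂₂)²) to d + √((u₁−p̂₁)² + (p̂₂−l₂)²).

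Coverage is the exact binomial probability of all outcomes whose interval contains the true value.

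**Single rate, mean coverage (%).**

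| n | Wald, p 0.05–0.95 | Wilson, p 0.05–0.95 | Wald, p 0.2–0.8 |
|---|---|---|---|
| 11 | 84.3 | 95.6 | 89.9 |
| 15 | 87.6 | 95.4 | 90.7 |
| 20 | 89.8 | 95.4 | 92.2 |
| 22 | 90.4 | 95.4 | 92.3 |
| 30 | 91.8 | 95.3 | 93.0 |
| 73 | 93.6 | 95.1 | 94.2 |
| 100 | 94.0 | 95.1 | 94.4 |

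Examples: 0/11 gives Wald 0 to 0% and Wilson 0 to 25.9%. For 1/11, Wald is 9.1 ± 17.0, or −7.9 to 26.1%; Wilson is 1.6 to 37.7%.

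**Rate difference, equal arms, coverage (%), Wald / Newcombe.**

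| n per arm | 0.1 vs 0.05 | 0.2 vs 0.1 | 0.5 vs 0.3 | Mean, all pairs 0.05–0.95 |
|---|---|---|---|---|
| 11 | 77.9 / 99.4 | 88.9 / 97.1 | 92.7 / 93.8 | 91.1 / 95.1 |
| 15 | 86.2 / 98.6 | 93.5 / 96.2 | 93.6 / 94.7 | 92.3 / 95.0 |
| 22 | 87.4 / 98.3 | 94.7 / 96.1 | 93.8 / 94.2 | 93.1 / 95.0 |
| 73 | 94.5 / 96.3 | 94.7 / 95.3 | 94.7 / 94.9 | 94.5 / 95.0 |

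At 11 per arm and 0.1 vs 0.05, the Wald difference has zero width with probability 0.9¹¹ × 0.95¹¹ = 0.314 × 0.569 = 17.8%.

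**Where the conclusion changes.** For 3/11 vs 0/11, d = 0.273.

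- Wald: 0.273 ± 1.96 × 0.134, or 1.0 to 53.6%, which excludes zero.
- Newcombe, from Wilson limits 9.7 to 56.6% and 0 to 25.9%: lower limit 0.273 − √(0.175² + 0.259²) = −4.0%, upper limit 56.6%.

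For 4/22 vs 0/22, Wald is 2.1 to 34.3% and Newcombe −0.2 to 38.5%.

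**The case against.** The strongest objection is that the small denominators are assumed. The documents give neither the baseline prevalence of dactylitis or enthesitis nor any expected response rate, and at full group size Wald is adequate. This stands, and it limits the weight of the point.

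The worst figures (77.9% coverage, 17.8% zero width) need both 11 per arm and rates of 5 to 10%, which nothing in the documents suggests. Both examples where Wald alone excludes zero need an arm with no responders. Averaged over rates of 0.2 to 0.8, Wald differences cover 91.9, 92.9 and 93.5% at 11, 15 and 22 per arm, against 94.5 to 94.7% for Newcombe: a gap of about 1 to 3 points. These mid-range figures are the fairer summary for differences.

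Starting from the SAP's 100 per group removes the case of 11 patients. Single-rate Wald coverage still averages only 88 to 92% at 15 to 30 patients.

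There are partial safeguards. SAP Table 4 prints baseline n/N by group for five of the six states, though PASDAS categories appear only in the pooled Table 1. Protocol 9.5 adds "Precision estimates will be used to determine appropriate sample sizes for the descriptive analyses". The first discloses small denominators without correcting the interval; the minimum sizes in 9.5 are set for therapy groups, not for outcome denominators.

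**Conclusion.** The concern holds, at modest importance. The Wald-only specification, the absence of a small-count rule and the restriction of six outcomes are all in the text. How small the denominators become is an assumption.

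With 11 to 22 qualifying patients per group, single-rate Wald intervals fall short of 95% by about 5 to 11 points on average over rates of 0.05 to 0.95, and by about 3 to 5 points over 0.2 to 0.8. Differences fall short by about 2 to 4 points on average, and by more only at very low or very high rates. The likely rows are dactylitis resolution and perhaps enthesitis resolution in Table 6. The other outcomes, and the pooled Table 3 with its larger denominators, are less affected.

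**What to change.** - Use Wilson score intervals for response rates in SAP Tables 3 and 6 and in protocol 9.7.
- Use the matching Newcombe interval for rate differences in SAP Table 6 and protocol 9.7.
- Print n/N beside each response rate.
- State in the Table 6 footnote how the p-value is obtained.

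The cost is wording in two documents and a standard software option, and nothing is lost if the subsets prove large. There are three drawbacks. The intervals are no longer symmetric about the estimate. Newcombe is conservative at very low rates (99.4% at 11 per arm, 0.1 vs 0.05). It can also disagree with the normal-approximation p-value: for 3/11 vs 0/11 the unpooled p is 0.042 while the Newcombe interval includes zero, hence the footnote.

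A separate documentation point carries no weight in the conclusion. The SAP outcome list puts cDAPSA low disease activity among the change outcomes, while Tables 3 and 6 report it as an achievement. The sponsor should reconcile these and state its denominator; the documents do not favour either reading.
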